- the Swal-QOL. This is a 44-items questionnaire is a highly valid instrument for evaluating and has a very reliable shorten reproducibility (Ginocchio D et al 2016). Its 11 subscales represents the different aspects of quality of life. The minimum and maximum score per subscale ranges from 0 to 100, indicating extremely impaired quality of life versus no impairment experienced by the individual;

- Visual Analogue Scale (VAS) for dysphagia: self-assessment of dysphagia severity will be rated from 0 (none) to 10 (worst imaginable) scale. Respondents will be classified as having no dysphagia (score 0), mild dysphagia (scores 1-4), moderate dysphagia (scores 5-6) and severe dysphagia (scores 7-10);
- the meal time.
- CGI (Clinical Global Impression Scale) scale for evaluating clinical changes after treatment (Busner et al 2007)

Two Speech Language Pathologists (SLPs) trained in dysphagia management will be involved: one, as evaluating speech therapist, will be blind on the NMES treatment and the other one as a treating speech therapist.

As far as the dysphagia concerned, patients will be considered dysphagic according to ASHA (score<6) and DYMUS (score >2).

The NICE guidelines (NICE 2014) identified from the literature a number of possible adverse events for NMES, which they classified under Safety section.

Those deemed likely were burning sensation, skin irritation or soreness beneath the electrodes and coughing or expectoration, neck or jaw pain and increasing severity of dysphagia. Incidences of these events were recorded during the NMES therapy. The therapists who delivered the NMES therapy were also asked to record any other adverse reactions. In addition, therapists were asked to record whether the adverse reaction was resolved by repositioning the electrodes.

Finally, the speech and language therapists were asked to note whether there was any change in the quality of the voice as a result of the NMES, as previous research has shown (Frost, 2018).

The training will consist of 16 sessions. After 8 (T1) every patient will be examined using: ASHA scale; VAS for dysphagia and meal time. After 16 (T2) sessions, every patient will be examined with both clinical and instrumental examinations; after 12 weeks (T3) from the end of treatment every patient will undergo clinical evaluations. At T3 the CGI will also be submitted to the pwSM caregivers

Rehabilitation treatment

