According to the presence of dysphagia, scored as previously described by ASHA and DYMUS scales, we estimate that, we can enrol 17 pwMS for each center.. The candidates will be randomly allocated (according to 2 blocked randomization lists, generated electronically by www.random.org) in two groups numbered consecutively and equal numbers will be allocated to the intervention group “standard rehabilitative treatment plus neuromuscular electrostimulation” (SRT-NMES), odd numbers to the control group “standard rehabilitative treatment plus Sham (SRT-S). Randomization will be done by single center.

Both SRT-NMES and SRT-S groups will be received 16 sessions of traditional dysphagia therapy according to their degree of dysphagia, contemporary associated with Sham or NMES, according to our previous experiences, two 30-min treatment a day, separated by a rest period of at least 45 minutes for four consecutive days per week, within a period of 4 weeks.

During the study period, steroids will not be permitted.

Patients who will experience relapses during the study period will be considered as drop-out.

Traditional dysphagia therapy

The training will be performed by expert speech therapists. Traditional dysphagia therapy (TDT) involved orofacial, lingual, and laryngeal motor exercises, including progressive resistance training, combination of lingual strengthening exercises, laryngeal adduction-elevation exercises, effortful swallow manoeuvre, Mendelsohn manoeuvre (Mendelsohn et al 1987), Masako manoeuvre (Fujii et al 1996) and Shaker exercises (Shaker et al 1997). Compensatory swallowing strategies included various modifications of head, neck, and body postures and adjustment of food/liquid temperature, viscosity, and volume. It may be necessary to whisk food completely or partially, often adding a thickening liquid in drinks to allow an adequate water intake for nutritional support.

(Gonzales-Fernandez et al 2008). The choice of specific positioning strategies and swallowing manoeuvres or exercises was based on the FEES findings and the clinical swallowing examination. The rehabilitative treatment will be administered in the 8 centers taking part to the study .

Neuromuscular electrostimulation (NMES)

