In the present study, VitalStim equipment will be used (VitalStim Therapy; Chattanooga Group, Chattanooga, TN, USA). Therapists received additional training and information on NMES by an experienced laryngologist certified to use surface electrical stimulation. The training was given according to the manual of the manufacturer, the VitalStim certification course (<http://www.vitalstim.com>).

Skin preparation and electrode placement will be in accordance with the manufacturer's instructions.

Channel 1 is horizontally immediately above thyroid notch. Channel 2 is parallel, below notch.

Having applied the electrodes, the amplitude of each channel of the stimulator will be increased and the subject will identify when they will be able just feel it. The amplitude will be then further increased until the subject will feel a 'grabbing sensation' which corresponded to muscular contraction. This will be the amplitude used for the therapy. This process will be repeated for the second channel of the stimulator. The typical electrical stimulus is at 80 Hz and at 300 microsec, and it will be adapted to avoid annoying stimulus to the patients.

During therapy, both channels will be active. In "sham" group the same electrodes will be positioned.

To maintain the double-blind study, the electrodes in the "sham" group will be placed in the same positions as the active treatment, with a current between 3 and 5 mA (average of 3.5 mA) until the patient begins to feel a slight tingling, current unable to perform muscle contraction. (Park J. S. et Al).

During electrical stimulation, traditional swallowing therapy will be carried out, by a trained speech therapist.

Before the study starting, the team of the 8 Centres, reached a consensus for the administration of clinical scales and how to score the FEES findings.

Briefly:

Subjects:

136 clinically definite MS subjects, both outpatients and inpatients (see inclusion and exclusion criteria below). Each patient will be informed on overall requirements of the study, and his/her written consent will be obtained

Primary Outcome:

The first aim of this study is to determine whether NMES adds benefit to a speech therapy traditional program. Performance between the groups will be compared at completion of treatment, after adjustment for baseline differences.

The mean difference at ASHA score between SRT-S vs SRT-NMES will represent the primary outcome.

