Secondary outcome will be the differences obtained at T0-T2 and T0-T3 in the two groups in DYMUS scale, FESS/DOSS score, the MNA, the Swallowing Quality of life questionnaire, Penetration and Aspiration Score, the Visual Analogue Scale and the Pooling score.

Hypothesizing a response to treatment in the 30% of the SHAM group and in 60% of active NMSE a sample size of 56 subjects for each group provides a power of 0.9 and a significance level of 5%. ($h = 0.6128748$, $n = 55.94774$, sig.level = 0.05, power = 0.9, alternative = two.sided)

We estimate we could have a dropout of approximately 10-15%. In this light we decided to enrol 136 pwMS (17 for each center) Baseline characteristics and comparability of the two treatment groups will be assessed by the two samples t-test for continuous variables and by chi-square or Fisher's exact test for categorical variables. To address the first aim of the study, will be used analysis of covariance comparing changes in study outcomes from baseline to T2 adjusting for differences in baseline measures of swallow performance, diet and quality of life across the two treatment arms. To evaluate the differences intra-group, we will performed longitudinal analyses using general linear models for repeated measures of outcome data collected at baseline to T2 .

Italian MS Society Research Foundation is funding the study

(Grant No 2019/R –Multi/ 005)

References

Alali D1, Ballard K2, Bogaardt H Treatment Effects for Dysphagia in Adults with Multiple Sclerosis: A Systematic Review. *Dysphagia*. 2016 Oct;31(5):610-8. doi: 10.1007/s00455-016-9738-2. Epub 2016 Aug 4.

American Speech-Language Hearing Association. National Outcomes Measurements System (NOMS): Adult Speech-Language Pathology Training Manual. Rockville, Md: American Speech-Language Hearing Association; 1998

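### The primary assessment T2 is triggered by the 16th session and has no calendar anchor, so a patient who stops early has no defined primary outcome measurement

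*Protocol*

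**What the plan says.** All three follow-up visits in Materials and methods (the paragraph just before Rehabilitation treatment) are tied to treatment received:

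- **T1:** "After 8 (T1) every patient will be examined using: ASHA scale; VAS for dysphagia and meal time".
- **T2:** "After 16 (T2) sessions, every patient will be examined with both clinical and instrumental examinations".
- **T3:** "after 12 weeks (T3) from the end of treatment every patient will undergo clinical evaluations".

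Under Primary Outcome the comparison is tied to the same event: "Performance between the groups will be compared at completion of treatment, after adjustment for baseline differences". The analysis paragraph that follows specifies an analysis of covariance of change from baseline to T2.

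On volume, Materials and methods says "The training will consist of 16 sessions". Rehabilitation treatment gives two half-hour treatments a day, "separated by a rest period of at least 45 minutes for four consecutive days per week, within a period of 4 weeks". Patients who relapse are to be counted as drop-outs. The sample-size paragraph allows for loss: "We estimate we could have a dropout of approximately 10-15" per cent.

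The protocol gives no date or window for T2, no rule for making up sessions, and no assessment for a patient who never reaches session 16.

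**The concern.** The aim is to learn whether adding NMES to swallowing therapy helps people with MS and dysphagia. That question covers everyone randomised, including those who cannot tolerate or do not finish the course. If the trigger for the primary visit is finishing the course, a site with a patient who stops at session 9 has no instruction to examine that patient at T2. The ASHA score needed for the primary analysis may then never be taken.

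This is a matter for the protocol. A statistical analysis plan can define populations and handle missing values, but it cannot supply a score that no site was told to collect.

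The loss could plausibly differ by arm. The section on neuromuscular electrostimulation raises the active current until the patient feels the muscle contract, while the sham current stops at a faint sensation. Materials and methods lists skin soreness, neck or jaw pain and worse dysphagia among the likely adverse events of NMES. If patients leave because of their treatment, the remaining groups are no longer the randomised ones.

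Patients who reach session 16 late do have a T2, but at a later time since randomisation, and their T3 moves with it.

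**Working it through.** **1. The plan's own sample size.** Inputs from the sample-size paragraph: response 30% (sham) and 60% (active), two-sided 5%, power 0.90.

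- h = 2·asin(√0.60) − 2·asin(√0.30) = 1.7722 − 1.1593 = 0.6129
- n = 2·((1.960 + 1.282)/0.6129)² = 55.95 per group, so 56 per group and 112 in all. The stated figure reproduces.
- Allowing for loss: 112/0.90 gives 125 and 112/0.85 gives 132. Enrolling 136 tolerates 1 − 112/136 = 17.6% loss.
- With 122 patients left (10% loss) or 115 (15% loss), power by the same formula is 0.923 or 0.908.

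Numbers suffice if loss stays within the stated range. The issue is which patients are measured, not how many.

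**2. When T2 falls.** Rehabilitation treatment gives 4 days × 4 weeks = 16 treatment days, and 16 × 2 = 32 half-hour treatments. The word *session* is not defined.

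| If one session is | Sessions available in 4 weeks | Earliest 16th session |
|---|---|---|
| a treatment day | 16 | end of week 4 |
| a half-hour treatment | 32 | day 8 of treatment, end of week 2 |

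A session count alone could therefore place T2 at week 2 or week 4.

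**3. Who has a T2.** Under the text as written:

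- a patient who reaches session 16 on schedule has T2 on schedule;
- a patient who misses some sessions and makes them up has a late T2 and a late T3;
- a patient who stops before session 16 has no T2. If at least 8 sessions were received there is an ASHA score at T1, but the primary analysis uses change to T2.

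**4. Size of the possible bias.** Let completers in an arm improve by C on average, stoppers by C − g, and let a proportion s stop. The mean over all patients is C − g·s, while the completers' mean is C. The completers' difference between arms is therefore too large by

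bias = g × (s_active − s_sham).

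The protocol gives neither g nor stop rates by arm, so every input here is an assumption:

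| Gap g (ASHA levels) | Active stop | Sham stop | Bias (levels, + favours NMES) |
|---|---|---|---|
| 1 | 15% | 5% | +0.10 |
| 2 | 15% | 5% | +0.20 |
| 1 | 15% | 0% | +0.15 |
| 2 | 15% | 0% | +0.30 |
| 1 | 10% | 10% | 0 |
| 1 | 5% | 15% | −0.10 |

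With 68 per arm, 15% and 5% stopping is 10.2 + 3.4 = 13.6 patients, or 10% of 136, the lower end of the loss the protocol expects.

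**The case against.** **The protocol says that every patient will be examined, and nothing limits the analysis to completers.** This is correct. A reader might infer from the primary-outcome wording that a completers-only analysis is planned. The documents do not support that: no such population is named, and population and missing-data rules may stand in an analysis plan not seen here. However, the every-patient wording is conditional on having had 16 sessions, so it does not tell a site what to do with someone who stopped. The risk remains; the assertion does not.

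**There may be ample slack in the schedule.** A reader might also infer that 16 sessions in 16 available days leaves no room for a missed day. That holds only if a session is a treatment day. If it is a half-hour treatment, half the slots are spare. Even on the first reading no weekdays are named, so a week's run of days might start later. Moreover, a patient who misses a day and makes it up has a late T2 rather than none, so the share of patients missing a day does not measure lost outcomes.

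**The direction of bias is guesswork.** Largely fair. The stimulus may be adapted for comfort, and therapists note whether moving the electrodes resolved a reaction. Sham patients who leave for lack of benefit could push the bias the other way. The expected drop-out is not split by arm or cause.

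**Measuring at the end of a completed course is a recognised design.** It is, and it suits a question about treatment received in full. It still needs a stated assessment for randomised patients who do not get there.

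**Conclusion.** The point holds in a limited form. T2 and the primary ASHA comparison depend on reaching session 16, with no calendar anchor and no assessment specified for patients who stop earlier. Those patients have no T2 under the text, and late finishers have T2 and T3 at varying times since randomisation. The consequence is a risk of a completers-only comparison, not proof of one.

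If stopping differs by arm, an illustrative bias is about 0.10 ASHA level (1-level gap, 15% against 5% stopping). It ranges from −0.10 to +0.30 over the assumed values tabulated. A reader might conclude that the result will favour NMES; the difference in stimulation intensity makes that plausible, but the protocol contains no figure that establishes either direction or size. It also gives no ASHA standard deviation against which to scale the bias. The sample-size calculation is not affected. The change is worth making because it determines whether primary data exist for patients who stop, and it is cheap.

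**What to change.** 1. State what one session is, reconciling Materials and methods with Rehabilitation treatment. This comes first, because the T1 and T2 dates depend on it.
2. Set T2 at a fixed time from randomisation or first session, at the planned end of the treatment period, with a short window. Set T3 at 12 weeks after the scheduled T2 date.
3. Perform T2 and T3 in every randomised patient regardless of sessions received.
4. Under Primary Outcome, replace the reference to completing treatment with *at T2, regardless of sessions completed*.
5. Record the number of sessions delivered as an adherence variable.
6. State whether patients counted as drop-outs for relapse are also assessed at T2 and T3.

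This is a wording amendment to the visit schedule, Rehabilitation treatment and Primary Outcome. It adds no examination, since those at T2 and T3 are already planned, and it does not alter treatment. The cost is that sites must recall patients who stopped, and the estimated effect may be slightly smaller than among completers.

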However, this type of treatment can be performed only in specialized centers and it is probably more invasive than NMES. In 2009, Bogaardt (Bogaardt et al 2009) conducted a Class IV trial with a sample of 25 patients with MS. The primary focus of the study was to examine the effects of NMES on pooling of saliva or liquid in the valleculae and pyriform sinuses. Six of the 25 patients had significant reduction in pooling of saliva in the pyriform sinuses, and 23 participants reported through a questionnaire that their swallowing had improved (Bogaardt, et al 2009). As far as we know, this is the unique paper focusing on the therapeutic effects of NMES in MS patients. Our research group recently published about the use of NMES in people with stroke and dysphagia. The methodology resulted safe with a good effectiveness in addition with traditional speech therapy. In fact, combined treatment seem to reduce the risk of penetration and aspiration in stroke dysphagic people. (Simonelli et al 2019).

The aim of the study is to determine whether NMES added benefit to a therapy program comprised of standard swallowing exercises in dysphagic pwMS

Materials and methods

The research plan will be implemented within a multi-center collaboration. Each of the 8 centers will recruit 17 inpatient and outpatient with a diagnosis of MS, according to revised McDonald criteria (Thompson et al 2018), with dysphagia. Each patient will be evaluated with a general and neurological evaluation scored according to the Expanded Disability Status Scale (EDSS) of Kurtzke and its functional systems.

Inclusion criteria will be:

- 1) Sex (both);
- 2) Age (older than 18)
- 3) Diagnosis: definite MS (Thompson et al 2018)
- 4) Stability: recruited subjects must be in a stable phase of the disease, without relapses which induce worsening > 1 point in the EDSS and with an EDSS <=8
- 5) ASHA<6 and DYMUS >2
- 6) Novelty: subjects should not have been trained with dysphagia program in the last 6 month
- 7) Mini-Mental State Examination: > 24;

Exclusion criteria will be:

- 1) dysphagia related to other diseases
- 2) presence of tracheal cannula
- 3) local or general contraindications to the use of equipment for electrical muscle stimulation of the neck
- 4) malignancies or acute inflammation in the anterior region of the neck.
- 5) lack of collaboration due to mental impairment

Baseline characteristics:

At T0, a clinical and instrumental examination will be suggested, concerning:

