- FEES, performed by a phoniatrician in a blinded way in order to verify: 1) rest status, with reports of possible secretions or food presence, particularly in the lower pharyngeal tract; 2) preliminary report on: a) glottis enclosure ability (phonation) b) coordination between breathing and vocalization, c) ability and sensitivity of the cough reflex. 3) "dry" swallowing, with observation of the pushing-back movement of the tongue, the time for swallowing voluntary activation(pharyngeal phase), the research of larynx elevation and epiglottis basculatory movement; 4) proposal of food coloured with green of varying consistencies to test the swallowing act with determined quantities: a) liquid: a spoonful, i.e. 10 ml, repeated three times; b) semisolid (gelatine consistency): a spoonful, i.e. 10 ml, repeated three times; c) solid: half a cracker, repeated with three bits. During each swallowing act, the observer will have to examine the same functions described above in point n. 3, and his/her attention will focus on premature falls of the bolus towards the pharynx, with or without penetration and/or aspiration; the word "premature" indicates that it is contemporary to the oral phase and is to be used to indicate the alimentary falls before the pharyngeal phase of swallowing; penetration and/or aspiration during the pharyngeal phase of swallowing; laryngeal

penetration, defined as passage of material into the laryngeal vestibule above the vocal folds and aspiration, defined as passage of material under the level of the true vocal folds; reports of the permanence of food and/or secretion in the lower tract of the pharynx after the pharyngeal phase of swallowing (pharyngeal residue or pooling) and evidence of penetration and/or aspiration of this residual component; the occurrence, or absence, of the cough reflex as a consequence of penetration and/or aspiration.

According to the FEES examination will be scored the severity of dysphagia through the Dysphagia Outcome and Severity Scale (DOSS Score) (O'Neil et al 1999). We'll also use the Penetration and Aspiration Scale (Rosembek et al, 1996) and the Pooling scale, able to evaluate the excess residue in the pharynx and larynx. (Farneti et al 2014). The FEES will be record by video.

- the DYMUS questionnaire (Bergamaschi et al., 2008)

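### The primary ANCOVA's named covariates leave out centre although allocation appears to be by centre, and three endoscopy-based T0–T3 outcomes have no examination at T3

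*Protocol*

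**What the plan says.** **Allocation.** Under Materials and methods, "Each of the 8 centers will recruit 17 inpatient and outpatient with a diagnosis of MS". Under Rehabilitation treatment, patients are allocated "according to 2 blocked randomization lists", and "Randomization will be done by single center". Block size is not given.

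**Primary analysis.** In the analysis paragraph near the end of the protocol, the arms are compared on change from baseline to T2 by ANCOVA, "adjusting for differences in baseline measures of swallow performance, diet and quality of life across the two treatment arms". The within-group repeated-measures model in the same paragraph also runs from baseline to T2. Centre appears in neither model.

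**Secondary outcomes.** These are "the differences obtained at T0-T2 and T0-T3 in the two groups" in seven measures: "DYMUS scale, FESS/DOSS score, the MNA, the Swallowing Quality of life questionnaire, Penetration and Aspiration Score, the Visual Analogue Scale and the Pooling score".

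**Source of three of these measures.** The description of the fiberoptic endoscopic examination (FEES), under Baseline characteristics, states: "According to the FEES examination will be scored the severity of dysphagia through the Dysphagia Outcome and Severity Scale" (DOSS). It then adds the Penetration and Aspiration Scale and "the Pooling scale, able to evaluate the excess residue in the pharynx and larynx".

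**Visits.** The schedule just before Rehabilitation treatment gives instrumental as well as clinical assessment at T2. At T3, 12 weeks after treatment ends, it gives clinical assessment only.

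**The concern.** *Centre.* When allocation is balanced within centre, differences between centres largely cancel out of the arm comparison. If the model has no centre term, those differences still sit in the residual variance. The reported standard error is then larger than the true sampling variation. The test stays valid but is conservative, and some power is given up. Whether this applies here depends on how the allocation text is read. It could instead mean that one centre carries out the randomisation, and two lists do not match eight centres (the 2 may be a block size).

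*T3.* A T0–T3 difference needs a T3 value. If endoscopy is not done at T3, the three scores it produces have none, and a statistical analysis plan cannot supply an examination that the visit schedule does not contain. In addition, neither stated model reaches T3.

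**Working it through.** **1. The plan's own figure.** For 30% against 60% responders, h = 2·asin(√0.6) − 2·asin(√0.3) = 0.61287. Then n = 2(z₀.₉₇₅ + z₀.₉₀)²/h² = 55.95, so 56 per group. This agrees with the protocol, and nothing below changes it.

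**2. Degrees of freedom.** 8 × 17 = 136 enrolled. At 15% loss 136 × 0.85 ≈ 116 remain. With intercept, arm and three baseline covariates, 116 − 5 = 111 residual df. Eight centres use 7 more, leaving 104.

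**3. Direction and ceiling of the effect.** Let ρ be the centre share of residual variance (ICC). With perfect balance within centre, the true variance of the arm difference is proportional to 1 − ρ, while the model without centre reports one proportional to about 1. The reported SE is therefore too wide by at most a factor of about 1/√(1 − ρ):
- ρ = 0.05: 1/√0.95 = 1.026
- ρ = 0.10: 1/√0.90 = 1.054
- ρ = 0.20: 1/√0.80 = 1.118

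The realised excess is smaller, because the odd 17 per centre and the dropout disturb the balance and there are only eight centres.

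**4. Simulation.** 60,000 trials per cell, 8 × 17 patients, 15% random loss, three baseline covariates in both models, normal outcome. The protocol gives neither the ICC nor an effect in SD units, so both are assumptions. The 0.61 SD is borrowed from the arcsine h and is not a documented ASHA effect.

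Allocation within centre, blocks of 2, effect 0.61 SD:

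| ICC | SE / true SD, no centre | Type I error, no centre | Power, no centre | Power, with centre |
|---|---|---|---|---|
| 0 | 0.994 | 5.0% | 89.4% | 88.9% |
| 0.05 | 1.010 | 4.8% | 89.7% | 90.2% |
| 0.10 | 1.035 | 4.2% | 90.5% | 91.8% |
| 0.20 | 1.070 | 3.6% | 91.3% | 94.3% |

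Blocks of 4 give SE ratios of 1.019, 1.035 and 1.073 at ICC 0.05, 0.10 and 0.20, with type I error 4.6%, 4.3% and 3.6%.

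Sensitivity to the assumed effect (power without → with centre, ICC 0.05 / 0.10 / 0.20):
- 0.5 SD: 75.0 → 75.9, 76.3 → 78.6, 77.1 → 82.8%, a gain of 0.9 / 2.3 / 5.7 points
- 0.7 SD: 96.0 → 96.2, 96.4 → 97.1, 96.9 → 98.2%, a gain of 0.2 / 0.7 / 1.3 points

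A separate run with one covariate and blocks of 4 gave type I error of 4.5%, 4.4% and 3.6% without centre at the same ICCs. At ICC 0.20 its power was 92.1% without and 94.9% with centre.

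**5. If allocation is one list across centres.** Type I error without centre is 4.9–5.0% throughout, so the stated model is already correct. Power at 0.61 SD without and with centre:
- ICC 0: 89.3 and 87.2%
- ICC 0.05: 89.5 and 88.8%
- ICC 0.10: 89.7 and 90.4%
- ICC 0.20: 89.9 and 93.5%

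Adding centre is then optional and can cost about 2 points.

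**6. T3, side by side.**

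| Secondary measure | Needs endoscopy? | Assessment type listed at T3? |
|---|---|---|
| DYMUS, MNA, Swal-QOL, VAS | No | Yes (clinical) |
| DOSS, Penetration and Aspiration, Pooling | Yes | No |

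The protocol keeps the two kinds of assessment apart: both are named at T0 and at T2, and the ASHA rating is described as not instrumental. Reading the T3 wording as including endoscopy would erase the contrast that the schedule draws between T2 and T3. So 3 of 7 measures have no scheduled source for a T3 value.

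**The case against.** The strongest case is against the centre point. The model is often settled in the statistical analysis plan, which is not at hand. The covariates are named as domains, not variables, and the list is not said to be closed. The gain depends on an uncertain reading of one sentence and on an ICC that the protocol does not give. The eight centres also agreed beforehand on how to administer the clinical scales and score the endoscopy, which should limit differences between them. ASHA is an ordinal scale from 1 to 7 with entry below 6, whereas the simulation uses a normal outcome.

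Much of this stands. It keeps the centre point to efficiency and consistency, makes the figures indicative only, and makes the remedy conditional. It does not remove the point: the protocol does state an adjustment set, and that set omits the factor by which it appears to allocate.

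On T3, it can fairly be said that only secondary outcomes are touched and that four of the seven measures, all T2 comparisons and the ASHA primary outcome are unaffected. The contradiction itself remains.

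**Conclusion.** Both parts hold, and both are minor.

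*Centre:* there is no bias, no type I inflation and no effect on the sample size. If allocation is within centre, the loss at an assumed 0.61 SD is about half a point of power at ICC 0.05, a little over one at 0.10 and three at 0.20. Over assumed effects of 0.5 to 0.7 SD, the range across those ICCs is 0.2 to 5.7 points. If allocation is not by centre, the stated ANCOVA needs no change.

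*T3:* this is the firmer part, because it rests on the text alone. Three of the seven T0–T3 secondary differences cannot be computed from the visits as scheduled.

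**What to change.** 1. State whether there is one blocked list per centre, what the 2 refers to, and whether the single-centre sentence means allocation within each centre or by one centre.
2. If lists are per centre, add centre (8 levels) to the primary ANCOVA alongside the baseline covariates already named. If not, leave it optional. This is a wording change that uses 7 of about 111 residual df. If allocation is by centre and centres do not differ, it costs about 0.5 points of power at 0.61 SD (0.2 to 0.7 over 0.7 to 0.5 SD).
3. Reconcile the secondary outcome list with the T3 visit for DOSS, Penetration and Aspiration, and Pooling, so that the listed time points match the examinations scheduled.
4. For the T0–T3 outcomes that are measured, state that the same baseline-adjusted comparison between arms applies, since both models now end at T2. This too is wording only.
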